10. HUMAN SUBJECTS

The subject population will include normal controls and individuals with existing diagnoses of schizophrenia. Men and women will be represented and ethnic representation in the sample groups will be determined by recruitment responses. Exclusion criteria for control subjects are psychiatric disorders in self or first degree relative, organic brain dysfunction, pregnancy or history of substance abuse. Psychiatric subject exclusion criteria are serious medical or neurologic illness, history of seizures, sustained loss of consciousness, substance abuse/dependence or pregnancy.

The drug evaluation studies will include normal subjects and individuals with existing diagnoses of schizophrenia. They will range in age from 18-35 years for all studies except those involving memantine, in which case they will range from 18-45 years. Males and females will be included in future studies. Subjects will be given a complete screening physical exam and will be excluded if showing any evidence of cardiovascular disease (e.g., hypertension, arrhythmia). Control subjects will also be screened for evidence of psychopathology or history of substance abuse using a modified SCID-N interview. If either is evident, the subject will be excluded from the study. All subjects will be informed of the nature of the study by a research assistant who will obtain consent if the subject wishes to participate. All subjects will be mentally competent and capable of giving informed consent.

Table 3. Proposed samples for ongoing / planned studies:

Study	Population	Total Sample	Rate	Status
"ONE-DAY" parametric studies	Normal Controls	up to 50/yr	50/yr	as needed
"WITHIN-SUBJECT" amphetamine/COMT	Normal Controls	120	60/yr	ongoing
"WITHIN-SUBJECT" memantine	Normal Controls	30	30/yr	ongoing
"WITHIN-SUBJECT" memantine	schizophrenia	60	24/yr	planned

The proposed study samples (Table 3) reflect both logistical and power consideration (see above, section "8. j. Statistics.") that differ across the several different studies covered by this application. Testing in the "ONE-DAY" session is designed for parametric "mini-studies", and the proposed sample of "up to 50 subjects" per year will allow us to study up to 5 different sets of stimulus parameters, with n's of 10 subjects per study. To study drug effects on PPI in normal control subjects, our target samples have historically been 20-30 subjects per dose; however, with the addition of COMT subgroup analyses, we currently plan to test 120 subjects in the within-subject amphetamine study, over a 2 year period (n=60/year). To study the effects of memantine on PPI and related measures in schizophrenia patients, we are proposing to study a total of 60 subjects: 30 per dose (10 and 20 mg). As this testing will be conducted over 2 - 3 years, we estimate recruitment needs of approximately 2 subjects per month, which will be easily accommodated by our recruitment capacity at the UCSD Medical Center, based on experience over the past 25 years.

Records and data will be rigorously protected, as described below. Aside from historical and questionnaire data, startle response, negative priming, MCCB, mismatch negativity and gamma band synchronization data will be obtained. Urine will be obtained for toxicological analysis as part of the subject exclusion process. Blood samples will be collected to identify genes that may be associated with PPI or its sensitivity to drugs.

The ethnic population in our male studies from the last 5 years (as we've only studied males exclusively based on drug study exclusion criteria) and is expected in the following years are:

Asian/Pacific Islander	29%
Black (not Hispanic)	3%
Hispanic	10%
White (not Hispanic)	56%
Other/unknown	2%

The ethnic population in our non-drug female studies from the last 5 years and is expected in the following years are:

Asian/Pacific Islander	12.5%
Black (not Hispanic)	2.5%
Hispanic	8.75%
White (not Hispanic)	72.5%
Other/unknown	3.75%

These numbers reflect the location of where we typically recruit subjects.

11. RECRUITMENT

1) Control subjects: Recruitment of clinically normal control subjects will follow our established and successful methods, using public announcements (e.g., newspapers and bulletin boards, online advertisements). Fliers that are posted and faxes that are sent to the UCSD Guardian (on-campus newspaper) are enclosed. Phone screening excludes subjects with a history of serious medical or neurologic illness or trauma, mental illness (including substance abuse), psychotropic medication use, known or suspected pregnancy or hearing problems. Screening is repeated at the time of testing, and a urine sample is collected for toxicological analysis (exclusion for illicit substances). The SCID is used with our published criteria to exclude theoretically "psychosis-prone" control subjects, important for

comparisons with schizophrenia patients. A handedness questionnaire is used to distinguish right and left handed subjects and a questionnaire for evaluating sexual preference is used to identify gender orientation, an important control in studies of sexual dimorphism of sensorimotor gating. Subjects also fill out cognitive and personality questionnaires: the Eysenck Personality Questionnaire (EPQ), Tridimensional Personality Questionnaire (TPQ), the Sensation Seeking Scale - Form V (SSS-V).

2) Schizophrenia patients: Recruitment of schizophrenia subjects will follow our established and successful methods. Patients will be recruited from the UCSD Outpatient Clinic, the UCSD VAMC clinics or community hospitals, and board and care facilities. Clinical assessment of schizophrenia patients follows our established procedures approved by the UCSD IRB for existing protocols (e.g. #071128, [name], PI; #071306, [name], PI). Specifically, after giving informed consent, some schizophrenia patients will be interviewed using the SCID-I/P to ensure that they meet the DSM-IV criteria for schizophrenia. Demographic information, including age, age of onset, duration of illness, number and duration of hospitalizations, socioeconomic status, education, a detailed medication history, medical and psychiatric history, and family history of schizophrenia disorders will be obtained. Positive and negative symptoms of schizophrenia will be assessed during the Schedule for the Assessment of Positive Symptoms (SAPS) and Schedule for the Assessment of Negative Symptoms (SANS). Inclusion criteria include: 1) DSM-IV diagnosis of schizophrenia; 2) Written informed consent to participate in the study; 3) Age > 18; 4) Absence of dementia or mental retardation; 5) Urine toxicology negative for recreational drugs; 6) Fluent and literate in English (needed for completion of MCCB). Exclusion criteria include: a) meets DSM-IV criteria for current substance abuse or dependence and has been substance abstinent for less than 30 days; b) a history of traumatic brain injury; c) auditory or visual impairments severe enough to prevent study participation.

Recruitment of female subjects: As per NIH guidelines, it is important to establish whether observed drug effects on these psychophysiological measures are sex-specific. Our current NIMH application thus proposes the use of female subjects in within-subject studies of drug effects on PPI, LI and related measures. At present, approval for studies in females is sought only for studies with amphetamine and memantine. Methods for these studies will be identical to those described above for male subjects, with the following exceptions: 1) urine pregnancy tests ("Surecheck Early Pregnancy Test") will be completed at the time of initial screening and test day 2 (exclusion: positive test); 2) testing will occur only during post-menses days 1-10; 3) blood will be drawn on the morning of testing and stored for possible later hormonal analyses using the GCRC/CTRI laboratory services; a total of 5 cc will be collected by venopuncture using GCRC/CTRI or hospital phlebotomy services.

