d) Subject payment (also see below, section 18): For subjects participating in the "Within-Subject" test sessions, payment will be divided in the following schedule: on completion of screening day: \$30; on completion of first TEST SESSION day: \$100; On completion of second TEST SESSION day: \$130. This payment schedule provides appropriate incentive for the subjects to return for the second test day. This is to ensure that subjects return for the second and third test days. If subjects fail screening criteria for recreational drug use prior to any TEST SESSION day, they will not be tested further and will not be paid for that test day. We will recommend that subjects remain in our laboratory for monitoring until six and one half hours after pill ingestion. Should they choose to leave our facility for any reason prior to that time, it will be at their own risk. Their involvement in the study will be completed and payment on the Test Session day will be prorated to \$16 per hour.

e) Venopuncture: Venopuncture for COMT allelic testing in some subjects will occur during the initial visit, before or after what normally is titled the SCREENING SESSION in the studies listed below. A single venopuncture performed by certified individuals within the UCSD Medical Center GCRC/CTRI or Blood Drawing Station will be used to 10 cc of blood for COMT allelic testing. Based on specific needs of the experimental design (e.g. equal number of Met/Met, Val/Met and Val/Val allelic carriers, or subgroups of "high" vs. "low" PPI levels, based on the upper vs. lower quartile of a normal population distribution), subjects may be asked to come back for further testing, if they indicate they would like to do so. If participants continue to the remainder of the study, there will be 2 test days, one of which will involve placebo, and the other day involving an active dose of amphetamine (20 mg), memantine (20 mg) or other approved test drug/dose. The TEST SESSIONS will mimic those in the WITHIN-SUBJECT model below; however, venopuncture occurs only during the first visit.

f) Clinical assessment: Specific clinical assessment tools used in control and schizophrenia subjects are described in Section 10.

g) Test schedules:

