1. The "WITHIN-SUBJECT" study involves a single drug. There will be 2 test days – on the additional test day, subjects will receive either placebo or an active dose of one of the following: amphetamine (20 mg), memantine (10 mg) and memantine (20 mg). Some studies may require a venopuncture for genetic analysis as discussed above. A "model" example of a WITHIN-SUBJECT test schedule is shown below:

Test Day 1

0815-0845 Subject signs required forms, provides urine sample, eats standardized breakfast, venopuncture (if required)

0845-0900 Vital signs (VS) check, hearing and vision test, symptom rating scale.

0900-0915 drug or placebo administration.

0915-0930 VS check; symptom rating scales.

0930-0945 EMG electrodes applied.

0945-1000 VS check; symptom rating scales.

1000-1125 Startle response measurement, including PPI, habituation and intensity assessment.

1125-1140 VS check; symptom rating scales.

1140-1155 Visual LI or Visuospatial priming or MCCB

1155-1210 VS check; symptom rating scales.

1210-1300 Subject offered lunch from cafeteria.

1300-1600 VS check hourly; subject dismissed if VS within established parameters at 1600.

Test Day 2: 7-30 days after Test Day 1

0815-0845 Subject signs required forms, provides urine sample, eats standardized breakfast, venopuncture (if required)

0845-0900 Vital signs (VS) check, hearing and vision test, symptom rating scale.

- 0900-0915 drug mg or placebo administration: WHICHEVER DOSE WAS NOT RECEIVED ON TEST DAY 1
- 0915-0930 VS check; symptom rating scales.
- 0930-0945 EMG electrodes applied.
- 0945-1000 VS check; symptom rating scales.
- 1000-1125 Startle response measurement, including PPI, habituation and intensity assessment.
- 1125-1140 VS check; symptom rating scales.
- 1140-1155 Visual LI or Visuospatial priming or MCCB
- 1155-1210 VS check; symptom rating scales.
- 1210-1300 Subject offered lunch from cafeteria.
- 1300-1600 VS check hourly; subject dismissed if VS within established parameters at 1600.

Subjects will be instructed to not eat on the morning of the test, and instead will be served a standardized meal 30 min prior to drug administration, so as to maintain a controlled and consistent impact on drug absorption.

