15. RISK MANAGEMENT PROCEDURES AND ADEQUACY OF RESOURCES

The overall risks of this proposal are small. Protection of subject confidentiality and privacy will be rigorously guarded by the assignment of coded numbers to each file in the computer analysis and database. Resulting data will not be released to any subject, and released only to a patient's primary physician when an appropriate release form is signed by the patient. The UCSD psychophysiology research laboratory of [name] has studied over 1000 control subjects and patients without any problems with confidentiality.

For the drug evaluation study, risk management procedures include: 1) Subjects will be asked to refrain from alcohol or other drug use while on the study. 2) Each subject will receive a complete history and physical examination prior to acceptance into the study. 3) A battery of psychological tests will be administered, as will an EKG and urine toxicology screen (which will also be used to test for pregnancy in drug studies including women of childbearing potential). 4) Subjects involved in studies with drugs will arrange for their transportation from the hospital, and any subject reporting any sedation upon completion of the study will be instructed to not operate a motor vehicle until the sedation is resolved. Subjects known or determined to have cardiovascular disease by EKG or patient history will be excluded. All subject information will be kept in a secure and locked area of the laboratory, CTF Building, UCSD Medical Center. Confidentiality will be protected to the extent provided by law.

If a participant has any questions regarding the study, they may contact the PI, [name]., Ph.D., Monday-Friday, 8 a.m. – 4:30 p.m. at [contact]. He may be reached after hours by contacting the UCSD operator at [contact] and having them page [name]. If any emergencies arise related to participating in these studies, the participant may proceed to the nearest emergency room or call 9-1-1.

Subjects will be told that they can terminate the experiment at any time if an aspect of the procedure causes them discomfort.

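### Urine pregnancy tests are listed for screening and test day 2 only, so one of the two dosing days has no explicitly listed same-day test

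*Protocol*

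**What the plan says.** Section 11 keeps the methods for women the same as for men, apart from a short list of exceptions. Item 1 of that list says that urine pregnancy tests "will be completed at the time of initial screening and test day 2 (exclusion: positive test". This is the only place in the available text that attaches days to the test.

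The test schedule in Section 9(g) has two dosing days, 7 to 30 days apart. Test Day 1 reads "0900-0915 drug or placebo administration"; on Test Day 2 the subject receives "WHICHEVER DOSE WAS NOT RECEIVED ON TEST DAY 1". Both mornings begin with the same line: "0815-0845 Subject signs required forms, provides urine sample, eats standardized breakfast". The schedule does not say what that urine is tested for.

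Three other places bear on the point:

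- Section 9(d), on payment: "If subjects fail screening criteria for recreational drug use prior to any TEST SESSION day, they will not be tested further".
- Section 15, item 3 of the risk management list, refers to a "urine toxicology screen (which will also be used to test for pregnancy in drug studies including women of childbearing potential". It gives no day.
- Section 14 requires a urine pregnancy test for all women in these studies, with exclusion if positive, again without a day.

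The SAP does not deal with pregnancy testing.

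**The concern.** Section 14 recognises that the study drugs could harm an unborn child. Its answer is a urine pregnancy test together with non-drug birth control. For the test to protect against exposure, a recent negative result has to be in hand before any dose that might be active. In this crossover each woman receives active drug on one of the two days, and the order is not known to those testing her. The rule with dates names only one dosing day. Staff who follow Section 11 as written could therefore give a possibly active dose on the other day without a same-day result. What is at stake is the safety of a small group, not the validity of any comparison.

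**Working it through.** No sample size, power or error rate is involved, so the check is a cross-reading of the schedule with some calendar arithmetic.

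**1. Which dosing day is uncovered?** Section 9(g) labels the dosing days Test Day 1 and Test Day 2. Section 9(d), however, explains the payment schedule with the sentence "This is to ensure that subjects return for the second and third test days", which makes sense only if screening is counted as the first day. Both numberings are set out below.

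| Numbering | Latest listed test before first dose | Latest listed test before second dose |
|---|---|---|
| Section 9(g) labels | Screening, age not stated | Same day |
| Screening counted as day 1 | Same day | Day of first dose, 7 to 30 days earlier |

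Under both, dosing days with a listed same-day test = 1, and 2 − 1 = 1 day has none. The Section 9(g) numbering is the likelier, because that is the only schedule in the protocol.

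**2. How old can the screening test be at the first dose?** No interval from screening to Test Day 1 is stated. Section 9(e) allows subjects to be called back after the initial visit according to genotype or PPI subgroup, so the gap need not be short. Section 11 limits testing of women to the first 10 days after menses. However old the screening result is, each dose should therefore fall within 10 days after a menses.

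**3. Does another section fill the gap?** Section 9(d) applies drug-use screening before any test session, Section 9(g) collects urine on both mornings, and Section 15 says that toxicology urine also serves for pregnancy testing. Put together, these could make the urine of each dosing morning a pregnancy sample. No one of them says that it is. Section 11, for control subjects, repeats screening at the time of testing but gives toxicology as the purpose of the urine. Section 10 excludes pregnancy without test times, and Section 9(i) describes the test kit without timing.

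**4. Is a same-day test feasible?** Urine is collected at 0815-0845 and the dose is given at 0900-0915. The shortest gap is 0900 − 0845 = 15 minutes and the longest is 0915 − 0815 = 60 minutes. The sample is already taken on 2 of 2 mornings.

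**5. Change in the number of tests.** Listed now: screening + test day 2 = 2. With both dosing days: 2 + 1 = 3. If the combined reading in step 3 is already the practice, the increase is 0.

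**The case against.** The strongest reply is that the listed times already form a coherent minimum. On the Section 9(g) labels, the screening test comes before the first dose and the test day 2 test comes before the second, so there is one new negative result before each dose. That stands. A reader might infer that the cycle window and birth control apply equally to both days and so leave the single test day unexplained; the documents do not support this, because screening supplies the test for the first dose. What remains is that this test has no stated maximum age. The one-test-per-dose logic also fails if screening is counted as day 1.

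A second reply is that Sections 9 and 15 together already provide a test on every dosing morning. This is a fair reading, and it rules out the stronger claim that no test would be done on Test Day 1. It is still an inference, since the only rule with dates leaves out a day. A reader might try to defeat it by noting that Section 15 also says "Each subject will receive a complete history and physical examination prior to acceptance into the study", as if the toxicology screen were confined to that time. That does not work: the sentence is item 2 of the list, while the toxicology screen is in item 3, which has no timing.

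A third reply is that the risk is small. This also stands. Dosing is confined to the days after menses, non-drug birth control is required, women are told to report an irregular cycle or suspected pregnancy, and active exposure is a single oral dose. The consent forms, which might give visit-level detail, are not in the text available for review.

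**Conclusion.** The point holds as a gap in the stated safety schedule: 1 of 2 dosing days has no explicitly listed same-day pregnancy test. On the more likely numbering it is Test Day 1, where a possibly active dose rests on a screening result of unspecified age. The documents do not show that a test would be omitted in practice, and the existing safeguards keep the absolute risk low.

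The risk cannot be put into figures. Section 9(c) says only that women enter a subset of studies, and neither their number nor the interval from screening to first dose is given. No endpoint, sample size or analysis is affected. The SAP reports memantine analyses as already completed, so the correction matters for any continuing or future dosing of women under this text. It is a minor point, worth acting on because the remedy costs so little.

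**What to change.** Change item 1 of the Section 11 paragraph on female subjects to require a negative urine pregnancy test at initial screening and before dosing on both Test Day 1 and Test Day 2, using the urine already collected at 0815-0845. A positive result means no dosing and exclusion. Add the test as a line on both days of the Section 9(g) schedule. For consistency, Sections 14 and 15 can point to the same timing.

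The cost is a wording change and at most one extra dipstick per woman (3 listed tests instead of 2). No extra visit or sample is needed.

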12. INFORMED CONSENT

Recruitment of subjects and informed consent procedures will follow [name] established methods. For all subjects we will have a consent form indicating any or all of the following procedures to be used: startle gating, mismatch negativity, gamma band synchronization, MCCB, negative priming and latent inhibition. Subjects included in drug studies will be told of any potential side effects they may expect from the drug to be used during testing. Specifically, all subjects will be asked to read a description of the test drug, modified from the Physician's Desk Reference, which includes the following information: 1) the typical indications for this drug; 2) the recommended starting dose for this drug, and details regarding typical maintenance doses and schedules; 3) common side effects experienced by individuals taking this drug, based on trials with the indicated clinical population; and 4) an assessment of the likelihood that they will experience significant side effects from this drug, in the doses to be used in this study. In all cases, fully informed consent will be obtained and [name] will be directly available to clarify any questions raised by a subject. Signed and witnessed consents will be kept on file with other patient data. The UCSD IRB has authorized no waivers or modifications of normal procedures.

Subjects will be carefully screened to ensure their ability to comprehend study procedures, risks, and benefits. Potential participants will be fully informed of all risks and benefits prior to giving their written informed consent and prior to enrollment in the study. Participants will be asked to repeat back understanding of this material, and if there is any question as to whether a person is able to provide informed consent then they will not be permitted to participate. A copy of the signed consent form will be stored in a separate locked filing cabinet from other de-identified coded materials, and a copy will be given to the study participant.

All study personnel involved in obtaining written informed consent will have completed a web-based course with post-test on Human Subject Research Protections and Good Clinical Practice, in addition to being trained by the Principal Investigator (PI) on obtaining informed consent. These study personnel will also be authorized to obtain informed consent by the IRB and Human Studies Subcommittee. Informed consent will be documented using standardized IRB-approved forms. The forms will be presented to all potential participants at the initial visit. Briefly, the informed consent form will describe the purpose of the study, procedures and participant involvement, nature of assessments and treatments, potential risks, alternatives to participation, costs and compensation, confidentiality, right to withdraw, potential benefits, relevant contact personnel, and information regarding the Health Insurance Portability and Accountability Act (HIPAA) of 1996. Because participation in the proposed study is entirely voluntary, patients can choose to discontinue the study at any point for any reason and this will in no way affect future medical treatment decisions or practices.

Genetic Testing, Material & Storage: One goal of this proposal is to identify single nucleotide polymorphisms associated with differential sensitivity to drug effects on sensorimotor gating and neurocognition in clinically normal and schizophrenia subjects. To accomplish this, blood samples will be sought from all subjects by venopuncture at the UCSD Medical Center. Five ml (less than half of a tablespoon) of blood will be collected. DNA will be extracted by the Genomics Core Laboratory at UCSD. Tubes will be stored in a -80 degree freezer located at the CTF room A-310. All samples will be identified only by their subject ID to ensure confidentiality.

Subjects will be fully informed of the risks involved in providing a sample for DNA testing. Subjects will be told that [name] will be responsible for how the blood specimen is used and that the specimens collected from the subjects and the DNA that they contain may also be used in additional research by [name]. However, neither the blood, DNA nor information that identifies the subject will be shared with any other entity or collaborator or other party outside of our immediate research lab at UCSD. It will not be shared with any member of their family. Subjects will also be told that none of the results of their genetic tests could provide meaningful information related to their likelihood of developing or transmitting any specific disorder or medical condition. Results of the research that are specific to the subject will not be shared with anyone whether they have authorized it or not. If any publication results, the subject's name will not be used.

